## 6.12.1.4. Sensitivity Analysis Related to the Treatment regimen Estimand

Sensitivity analyses of the primary efficacy outcomes will be conducted using the FAS and guided by the "treatment-regimen" estimand, which represents the efficacy irrespective of adherence to study drug. This assessment will analyze percent change in body weight obtained at the 52-week visit using an ANCOVA and the percentage of participants achieving at least 5% body weight reduction obtained at the 52-week visit using a logistic regression model. The terms for both models will be the same as specified in Section 6.12.1.2 for "treatment regimen" estimand.

Missing values of change in body weight at the 52-week visit will be imputed based on observed body weight change from baseline values at the visit from participants in the same treatment group who had their efficacy assessed after early discontinuation of study drug. In cases where there are not enough retrieved dropouts to provide a reliable imputation model (for example, the model implemented by the SAS program does not converge), an alternative multiple imputation method with reference to the placebo group (placebo multiple imputation) will be used. Analysis will be conducted with multiple imputations.

## 6.12.2. Secondary Efficacy Analyses Subject to Type 1 Error Rate Control

Table GPIA.6.3.

# 6.12.3. Type 1 Error Rate Control Strategy for Primary and Key Secondary Efficacy Analyses

Type I error rate control strategy for evaluation of primary and key secondary objectives is performed in "efficacy" estimand as efficacy analysis is for China registration purpose, which is illustrated in Figure GPIA.6.1. The hypotheses for the primary and key secondary objectives are as follows:

- $H_{10,1}$  and  $H_{15,1}$ : superiority of tirzepatide 10 mg and/or 15 mg versus placebo for percent change in body weight from randomization and percentage of participants who achieve  $\geq 5\%$  body weight reduction at 52 weeks
- H10,2 and H15,2: superiority of tirzepatide 10 mg and/or 15 mg versus placebo for change in body weight (kg) from randomization at 20 weeks.
- $H_{10,3}$  and  $H_{15,3}$ : superiority of tirzepatide 10 mg and/or 15 mg versus placebo for percentage of participants who achieve  $\geq 10\%$  body weight reduction from randomization at 52 weeks
- $H_{10,4}$  and  $H_{15,4}$ : superiority of tirzepatide 10 mg and/or 15 mg versus placebo for percentage of participants who achieve  $\geq 15\%$  body weight reduction from randomization at 52 weeks
- H10,5 and H15,5: superiority of tirzepatide 10 mg and/or 15 mg versus placebo for change from randomization in waist circumference (cm) at 52 weeks

[figure not shown]

Figure GPIA.6.1 Type 1 error control strategy for primary and key secondary efficacy endpoints.

Abbreviations: PWL = percent weight loss WC = waist circumference; wk = week, WT = weight loss in kg

## 6.12.4. Other Secondary and Exploratory Efficacy Analyses

Other secondary and exploratory efficacy analyses will be conducted for EAS. Missing data will be imputed using LOCF or handled through MMRM without utilizing multiple imputation technique, except for mean change in fasting lipids (mmol/L) from randomization (total cholesterol, LDL cholesterol, HDL cholesterol, non-HDL cholesterol, VLDL cholesterol, triglycerides, free fatty acids), the analysis related to "efficacy estimand will be conducted in the EAS and "treatment regimen" estimand will be conducted using data in the FAS.

## 6.12.4.1. Other Secondary Efficacy Analyses

Table GPIA.6.4.	Secondary	y Measures Not Controlled for Type 1 Error
	occontail	

Objective	Relative to the efficacy measure:	Analysis conducted in a manner similar to:	Additional Information
Tirzepatide10 mg and/or 15 mg QW is superior to placebo	Mean change in body weight (kg) from randomization	MMRM model in Section 6.12.1.1	LSM estimates through 52 weeks will be plotted by study treatment.
at 52 weeks:	Mean change in BMI (kg/m  ) from randomization	MMRM model in Section 6.12.1.1	Use baseline BMI (kg/m  ) as a covariate. LSM estimates through 52 weeks will be plotted by study treatment.
	Mean change in HbA1c (%, mmol/mol) from randomization	MMRM model in Section 6.12.1.1	Use baseline HbA1c (%, mmol/mol) as a covariate. LSM estimates through 52 weeks will be plotted by study treatment.
	Mean change in fasting glucose (mg/dL) from randomization	MMRM model in Section 6.12.1.1	Use baseline fasting glucose as a covariate. LSM estimates through 52 weeks will be plotted by study treatment.
	Mean change in SF-36v2 acute form physical functioning domain score from randomization	ANCOVA model	with terms of treatment, stratification factors, and baseline SF-36v2 PF score as a covariate. Missing data will be imputed using LOCF method.
	Mean change in IWQOL- Lite-CT Physical Function composite (PF) score from randomization	ANCOVA model	with terms of treatment, stratification factors, and baseline IWQOL-Lite CT PF score as a covariate. Missing data will be imputed using LOCF method.
Tirzepatide QW (all doses combined) is superior to placebo at 52 weeks	Mean change in DBP (mmHg), SBP (mmHg), fasting lipids (mmol/L): total-C (mg/dL), LDL-C (mg/dL), HDL-C (mg/dL),	MMRM model in Section 6.12.1.1	All tirzepatide doses will be pooled together. LSM estimates through 52 weeks will be plotted by study treatment.
	non-HDL-C, VLDL-C (mg/dL), triglycerides (mg/dL), free fatty acids (mg/dL), fasting insulin from randomization	ANCOVA model	with terms of treatment, stratification factors, and baseline value of lipid parameter as a covariate. Missing data will be imputed using method described in 6.12.1.3.

Abbreviations: BMI = body mass index; DBP = diastolic blood pressure; HbA1c = hemoglobin A1c; HDL-C = high-density lipoprotein cholesterol; IWQOL-Lite-CT = Impact of Weight on Quality of Life-Lite-Clinical Trials Version; LDL = low-density lipoprotein; LOCF = last observation carried forward; LSM = least squares mean; MMRM = mixed model for repeated measures; QW = once-weekly; SF-36v2 = Short Form 36 version 2 Health Survey; VLDL-C = very low-density lipoprotein cholesterol.

## 6.12.4.2. Exploratory Efficacy Analyses

Objective	Relative to the efficacy measure:	Analysis Conducted
compare tirzepatide 10 mg, and/or 15 mg with placebo at 52 weeks compare tirzepatide 10	Percentage of participants achieving ≥20% and 25% body weight reduction from randomization Percentage of participants whose BMI shifts	Longitudinal logistic model in Section 6.12.1.1 Shift analysis will be conducted
mg, and/or 15 mg with placebo at 52 weeks	between clinically relevant categories, ie, from baseline ( $<28, \ge 28$ ) to postbaseline ( $<24, \ge 24$ and $<28, \ge 28$ )	based on data from EAS.
visualize tirzepatide10 mg and/or 15 mg with placebo percent weight loss change from randomization up to safety follow-up after 52 weeks	Percent body weight loss measured at postbaseline from randomization to 52 weeks plus 4 weeks safety follow-up	Time-course plot will be generated. Only the participants who complete the 52 weeks treatment and have the safety follow-up (Visit 801) will be included.
compare tirzepatide 10 mg, and/or 15 mg to placebo at 52 weeks:	
 
SF-36v2 acute form Mental Component Score (MCS)
 
SF-36v2 acute form Physical Component Score (PCS)
 
SF-36v2 acute form Role-Physical domain (RP)
 
SF-36v2 acute form Bodily Pain domain (BP)
 
SF-36v2 acute form General Health domain (GH)
 
SF-36v2 acute form Vitality domain (VT)
 
SF-36v2 acute form Social Functioning domain (SF)
 
SF-36v2 acute form Role-Emotional domain (RE)
 
SF-36v2 acute form Mental Health domain (MH)
 
IWQOL-Lite-CT total score
 
IWQOL-Lite-CT Physical composite score
 
IWQOL-Lite-CT Psychosocial composite score
 
EQ-5D-5L utility score
 
EQ-5D-5L VAS score
 
	Only data from participants from EAS will be included. ANCOVA model with terms of treatment, stratification factors, and baseline score as a covariate. Missing data will be imputed using LOCF method.

 Table GPIA.6.5.
 Exploratory Efficacy Analysis

Abbreviations: BMI = body mass index; EAS = Efficacy Analysis Set; IWQOL-Lite-CT = Impact of Weight on Quality of Life-Lite-Clinical Trials Version; MMRM = mixed model for repeated measures; QW = once weekly; T2DM = type 2 diabetes mellitus; VAS = Visual Analog Scale.

In addition, the following endpoints, risk difference in proportions for an unconditional treatment effect (Ge et al.2011) among each tirzepatide dose and placebo arm may be conducted:

• percentage of participants achieving at least 5% body weight reduction at 52 weeks

- percentage of participants achieving at least 10% body weight reduction at 52 weeks
- percentage of participants achieving at least 15% body weight reduction at 52 weeks
- percentage of participants achieving at least 20% body weight reduction at 52 weeks.
- percentage of participants achieving at least 25% body weight reduction at 52 weeks.

## 6.13. Safety Analyses

Unless specified otherwise, safety assessments will be based on the SS (Table GPIA.6.1). All events that occur between the first dose date of study drug and the end date of study participation will be included, regardless of the adherence to study drug.

The statistical assessment of homogeneity of the distribution of categorical safety responses between tirzepatide doses and placebo will be conducted using Fisher's exact test, unless specified otherwise.

For the selected continuous safety parameters, the mean change from baseline differences vs. placebo will be assessed via an MMRM using REML. Data from scheduled visits will be utilized for this analysis unless specified otherwise, the model for the analysis during 52 weeks treatment period will include sex, presence of comorbidities at randomization, treatment group, visit and treatment-by-visit interaction as fixed effects, and baseline value of the safety parameter as a covariate. To model the covariance structure within participants, the unstructured covariance matrix will be used. If this model fails to converge, the covariance structures specified in Section 6.12.1.1 will be tested in order until met convergence. If the data does not warrant the MMRM model, then ANCOVA model will be conducted.

For selected safety parameters, time-to-first-event analysis via the Cox-proportional hazards model may be conducted. Participants without the event will be censored at the end of study participation. For participants experiencing the event, the "time-to-first-event" will be the time (in days) from first dose to first occurrence of the event.

Where necessary, the rate of events will be analyzed using a generalized linear mixed-effects model assuming the number of events follow a negative binomial distribution and with treatment as a fixed effect. The logarithm of days during the active treatment period will be adjusted as an offset to account for possible unequal treatment duration of follow-up between participants.

Unless otherwise specified, all the analyses listed in this section will be conducted using SS in the postbaseline period: up to 52 weeks treatment period plus the safety follow-up (Visit 801, if applicable) for all randomized participants.

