# 6. A Priori Statistical Methods

## 6.1. Populations for Analyses

For purposes of analyses, Table GPIA.6.1 defines the analysis sets.

 Table GPIA.6.1.
 Description of Analysis Datasets

Analysis Set	Description
Entered Participants	All participants who sign informed consent
Randomized Participants	All participants who are randomly assigned a study treatment
Modified Intent-to-Treat (mITT) Set	All randomly assigned participants who are exposed to at least 1 dose of study drug. Participants will be included in the treatment group they were randomized to.
Efficacy Analysis Set (EAS)	Data obtained during treatment period from mITT, excluding data after discontinuation of study drug (last dose date + 7 days).
Full Analysis Set (FAS)	Data obtained during treatment period from mITT, regardless of adherence to study drug.
Safety Analysis Set (SS)	Data obtained during the treatment period plus safety follow-up period from mITT, regardless of adherence to study drug.
Per Protocol Set (PPS)	Participants included in the randomized population who have completed Week 52 of study treatment without permanent discontinuation of IP and without significant protocol deviations through Week 52 that would significantly impact the primary objective.
	Treatment group will be defined on the basis of the treatment the participants actually receive.

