### 6.13.3.4.2. Liver Enzymes

Analyses for laboratory analyte measurements are described in Section 6.13.6. This section describes additional analyses of liver enzymes.

The counts and percentages of participants with the following elevations in hepatic laboratory tests at any time during the treatment period and during the entire study including follow up period will be summarized between treatment groups:

- The counts and percentages of participants with an alanine aminotransferase (ALT) measurement ≥3 times (3x), 5 times (5x), and 10 times (10x) the Covance ULN will be summarized for all participants with a postbaseline value and for subsets based on various levels of baseline value.
  - participants whose nonmissing maximum baseline value is ≤1x ULN
  - $\circ$  participants whose maximum baseline is >1x ULN, and
  - participants whose baseline values are missing.
- The counts and percentages of participants with an aspartate aminotransferase (AST) measurement ≥3x, 5x, and 10x the Covance ULN during the treatment period will be summarized for all patients with a postbaseline value and for subsets based on various levels of baseline, as described above for ALT.
- The counts and percentages of participants with a total bilirubin (TBL) measurement ≥2x the Covance ULN during the treatment period will be summarized for all participants with a postbaseline value, and subset into 4 subsets:
  - participants whose nonmissing maximum baseline value is  $≤1 \times ULN$
  - $\circ$  participants whose maximum baseline is >1 x ULN, but <2 x ULN
  - $\circ$  participants whose maximum baseline value is  $\geq 2 \times ULN$ , and
  - o participants whose baseline values are missing.
- The counts and percentages of participants with a serum alkaline phosphatase (ALP) measurement ≥2x the Covance ULN during the treatment period will be summarized for all participants with a postbaseline value and for the subsets described above to TBL.

Maximum baseline will be the maximum non-missing observation in the baseline period. The maximum value will be the maximum non-missing value from the postbaseline period. Planned and unplanned measurements will be included.

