### 6.13.3.6.2. Definitions of Immunogenicity Assessment Periods

Immunogenicity Baseline Observations: Baseline period for immunogenicity assessment for each participant includes all observations on or prior to baseline visit. In instances where multiple baseline observations are collected, to determine participant ADA status the last nonmissing

immunogenicity assessment prior to first administration of study is used to determine treatmentemergent status (see below).

Immunogenicity Postbaseline Period Observations: Postbaseline period observations for each participant includes all observations after the first administration of study drug. There are two different periods listed below:

- The planned treatment period is defined as from the first dose of treatment to end of the treatment period
- The entire postbaseline period is defined as from the first dose of treatment to the end of safety follow-up visit or date of study withdrawal

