## 6.13.6. Clinical Laboratory Evaluation

Limits from the performing lab will be used to define low (L) and high (H). Descriptive summaries by treatment and by nominal visit will be provided for the baseline and postbaseline values as well as the change from baseline values. The associated descriptive will be presented in System International (SI) units and in conventional (CN) units.

Observed and change from baseline values for each visit may be displayed in plots for participants who have both a baseline and at least 1 postbaseline planned measurement. Baseline will be the last nonmissing observation prior to taking first study drug. Unplanned measurements will be excluded from plots.

A shift table will be provided including unplanned measurements. The shift table will include the number and percentage of participants within each baseline category (low, normal, high, or missing) versus each postbaseline category (low, normal, high, or missing) by treatment. The proportion of participants shifted will be compared between treatments using Fisher's exact test.

For qualitative laboratory analytes, the number and percentage of participants with normal and abnormal values will be summarized by treatment.

A listing of abnormal findings will be created for laboratory analyte measurements, including qualitative measures. The listing will include participant identification, treatment group, laboratory collection date, study day, analyte name, and analyte finding.

The MMRM model or ANCOVA (if MMRM model is not applicable) will be used for the analysis during the treatment period for the continuous measurements for selected lab tests.

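### The safety event-rate model counts events through Visit 801, but its offset is days in an undefined active treatment period

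*SAP*

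**What the plan says.** SAP Section 6.13 fixes the event window twice. Its opening paragraph states: "All events that occur between the first dose date of study drug and the end date of study participation will be included", whether or not the participant stayed on drug. Its closing paragraph sets the default period for the section as "up to 52 weeks treatment period plus the safety follow-up (Visit 801, if applicable) for all randomized participants". Section 6.1 defines the Safety Analysis Set the same way: "Data obtained during the treatment period plus safety follow-up period from mITT, regardless of adherence to study drug". Section 6.2 ends participation at the earliest of death, withdrawal or Visit 801.

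Between those two paragraphs stand two event models:

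- **Cox model for time to first event:** "Participants without the event will be censored at the end of study participation".
- **Negative binomial model for event rates, to be run where needed:** "The logarithm of days during the active treatment period will be adjusted as an offset to account for possible unequal treatment duration of follow-up".

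The SAP does not define *active treatment period*. The nearest terms are:

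- Protocol Section 5.1.1.2.2, where the treatment period runs from the end of Visit 2 to Visit 15 (week 52).
- SAP Section 6.13.3.6.2, for immunogenicity only: "The planned treatment period is defined as from the first dose of treatment to end of the treatment period".
- SAP Section 6.10.1, which defines duration on study treatment (first dose to last dose plus 7 days) separately from duration of follow-up (randomization to last visit).

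Protocol Section 5.1.1.2.3 states that no study drug is given in the safety follow-up.

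**The concern.** An offset should measure the time in which the counted events could have occurred. Here the count runs to the end of participation, while the offset stops with active treatment, and no sentence limits the count to that shorter period. The two event models in Section 6.13 therefore use different time at risk.

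The undefined term adds a second problem. Read as the 52-week period, the offset omits only the four follow-up weeks. Read as time on drug, it also omits all the time after a participant stops drug but stays in the study, and Protocol Section 8.1.1 asks such participants to attend every remaining visit. Two programmers could build different offsets and both claim to follow the SAP.

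What is at stake is the absolute event rates and, if stopping differs between arms, the rate ratio. The SAP plans to report rates of hypoglycemia (Section 6.13.3.5) and injection site reactions (Section 6.13.3.8). Neither section names a model, but this is the only rate model in the SAP's safety section.

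**Working it through.** The plan gives no figure for this model, so there is none to reproduce.

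**Inputs from the documents.** 52 weeks of treatment plus 4 weeks of follow-up, 56 weeks in all. Visit 801 falls four weeks after the early discontinuation (ED) visit for those who leave and decline Visit 99.

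**Assumptions.** The true event rate is 1 on drug and *r* off drug, equal in both arms. A fraction *p* stops at week *t*: 25% in one arm, 10% in the other, at week 8 or 40. The documents give only a single 25% dropout rate, used for power.

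**Formula.** Crude rate = expected events / total offset weeks. With a matched offset and *r* = 1 it equals 1.

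**Reading A: offset covers the 52-week period**

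A completer has (52 + 4*r*)/52:
- *r* = 1: 56/52 = 1.077
- *r* = 0.5: 54/52 = 1.038
- *r* = 0: 1.00

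If everyone is followed to week 56, the inflation is equal across arms and the rate ratio is 1.00.

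If stoppers leave the study at *t* + 4 and *r* = 1, events per participant are 56(1 − *p*) + *p*(*t* + 4). The result depends on where a leaver's offset ends:

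| Leaver's offset ends at | *t* | 25% arm | 10% arm | Ratio |
|---|---|---|---|---|
| ED visit | 8 | 45/41 = 1.098 | 51.6/47.6 = 1.084 | 1.012 |
| ED visit | 40 | 53/49 = 1.082 | 54.8/50.8 = 1.079 | 1.003 |
| Visit 801 or week 52, whichever is earlier | 8 | 45/42 = 1.071 | 51.6/48 = 1.075 | 0.997 |
| Visit 801 or week 52, whichever is earlier | 40 | 53/50 = 1.060 | 54.8/51.2 = 1.070 | 0.990 |

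**Reading B: offset covers days on drug, stoppers followed to week 56**

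Offset weeks are 52(1 − *p*) + *pt*. The remaining weeks up to 56 contribute events at rate *r*.

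| *t* | *r* | 25% arm | 10% arm | Ratio |
|---|---|---|---|---|
| 8 | 1 | 56/41 = 1.366 | 56/47.6 = 1.176 | 1.161 |
| 40 | 1 | 56/49 = 1.143 | 56/50.8 = 1.102 | 1.037 |
| 8 | 0.5 | 48.5/41 = 1.183 | 51.8/47.6 = 1.088 | 1.087 |
| 40 | 0.5 | 52.5/49 = 1.071 | 53.4/50.8 = 1.051 | 1.019 |
| either | 0 | 1.00 | 1.00 | 1.00 |

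Swapping the arms inverts the ratio: 1/1.161 = 0.861 and 1/1.037 = 0.964. Equal stopping gives 1.00.

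**Checks with the model itself**

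- A large-sample negative binomial fit (0.5 events per 52 weeks, dispersion 1, *r* = 1) agrees on Reading A: rate inflated by 1.077 with ratio 1.00 when all are followed to week 56. With leavers the ratio is 1.003 to 1.017 (offset to ED visit) or 0.990 to 0.996 (offset to Visit 801 or week 52). On Reading B it gives 1.04 (*t* = 40) to 1.28 (*t* = 8).
- A simulation of Reading B used 70 per arm, 1,000 runs, 2 events per 52 weeks, dispersion fixed at 1, *r* = 1 and 25% versus 10% stopping. The mean ratio was 1.27 with stopping at week 12 and 1.11 at week 26, with rejection of 28.7% and 8.4% at nominal 5%. With the offset matched to the count, the ratio was 0.99 in both cases, with rejection of 6.5% and 5.0%. Holding the dispersion fixed probably contributes to the excess rejection (14.8% even with 25% stopping in both arms at week 12), so those percentages are only indicative.

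**The case against.** The best reply is that the phrase about active treatment sets the window for the whole rate analysis, count included. The closing default in Section 6.13 yields where something else is specified, and the section's own MMRM paragraph narrows its window in passing to the 52-week treatment period. Section 6.13.6 does likewise: the model "will be used for the analysis during the treatment period for the continuous measurements for selected lab tests". On that drafting habit there would be no mismatch. This is arguable, but those sentences attach the window to the analysis, whereas the rate sentence attaches it to the offset alone. Section 6.13.3.4.2 shows that the SAP can name its windows expressly: "at any time during the treatment period and during the entire study including follow up period will be summarized between treatment groups". If a restriction of the count was meant, it still has to be written.

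Other points against carry weight:

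- The offset sentence speaks of treatment duration of follow-up, which mixes the two durations that Section 6.10.1 keeps apart. Loose wording is as likely as a deliberate choice of on-drug time.
- The larger ratios need Reading B, unequal stopping, retained stoppers and continuing off-drug events together. The documents state no difference in dropout between arms.
- Little depends on the model. It runs only if needed, no named endpoint is tied to it, and between-arm comparisons of categorical safety responses default to Fisher's exact test.
- The SAP uses last dose plus 7 days for exposure and for the Efficacy Analysis Set, not for counting adverse events. Using it for an on-treatment event rate would be a new choice.

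These limit the consequence. They do not bring the two windows into line.

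**Conclusion.** The point holds: as written, the rate model's count and offset cover different windows. The mismatch arises on either reading of the undefined term, because the drug-free follow-up is in the count and outside the offset.

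The 52-week reading is the more natural one. There the absolute rate for a completer is overstated by 0% to 7.7% as the off-drug event rate goes from nil to unchanged, and the crude rate ratio stays within 0.990 to 1.012 under the assumed stopping. On the on-drug reading the rate ratio can be biased in either direction: crude values of 1.02 to 1.16, or their inverses, when off-drug events continue at half to the full rate, and more in a fitted model under some assumed rates and dispersions. Those figures illustrate the mechanism and are not predictions.

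The correction should be made, but the issue is confined to safety event rates. Primary and key secondary analyses, Fisher's exact tests and the sample size are untouched.

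**What to change.** Replace the offset sentence in SAP Section 6.13 with one that defines the period and applies it to both count and offset. For rates regardless of adherence, use the log of days from first dose to end of study participation as defined in Section 6.2. This matches the section's event window and the Cox model's censoring, and it returns a completer's factor to 56/56 = 1.00.

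If an on-treatment rate is also wanted, state it as a separate analysis and restrict both count and offset to one named window. First dose to last dose plus 7 days is already the SAP's exposure definition in Section 6.10.1. Another window would serve equally well if it governs both.

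The cost is one SAP sentence. No new data are needed.
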